10.2 Risk Minimization

Refer to "Prevention and Mitigation" column in the table under **Section 10.1**.

10.3 Potential Benefits

The main benefit of this study is that subjects may experience improved glucose control. They may gain increased awareness of emerging technologies for diabetes management as a result of their participation.

10.4 Risk-Benefit Rationale

The main benefit of this study is that subjects may experience improved glucose control. With all closed loop insulin pumps, there is a risk that the pump will deliver too much or not enough insulin, resulting in hypoglycemia or hyperglycemia. These risks have been minimized through previous characterization of the performance of the 780G system and a variety of safety checks that are an integral part of the 780G closed loop algorithm.

10.5 Risk Determination

In the opinion of the sponsor, this study is considered to be a significant risk (SR) study. Results of an evaluation of the requirements per 21 CFR Part 812.3, led to the SR determination as follows:

- The devices present potential for serious risk to subject health, safety, or welfare.
- The devices are for a use of substantial importance in treating disease, and presents potential for serious risk to subject health, safety, or welfare.

Therefore, submission of an Investigational Device Exemption (IDE) application to the United States FDA is required.

11. Adverse Events

11.1 Adverse Events

Throughout the course of the study, investigational centers will make all efforts to remain alert to possible reportable adverse events (AEs) or untoward findings. The study personnel will elicit reports of AEs from the subject at each visit (including phone calls) starting at the time of signing the informed consent documenting the medical diagnosis, date of event start and end, causality (relationship to device or procedure), treatment, outcome, assessment of seriousness, and description that includes the details of the event.

11.2 Definitions and Classification of Adverse Events

Medtronic uses the definitions provided in ISO 14155:2020 and 21 CFR 812 for AE definitions. Where the definition indicates "device", it refers to any device used in the study. This might be the device under investigation, or any market released component of the system.

Severe Hypoglycemia is an event requiring assistance of another person due to altered consciousness to actively administer carbohydrate, glucagon, or other resuscitative actions.^[5]

This means that the subject was impaired cognitively to the point that he/she was unable to treat himself or herself, was unable to verbalize his or her needs, and was incoherent, disoriented and/or combative.

These episodes may be associated with sufficient neuroglycopenia to induce seizure or coma. Plasma glucose measurements may not be available during such an event, but neurological recovery attributable to the restoration of plasma glucose to normal is considered sufficient evidence that the event was induced by a low plasma glucose concentration. ^[5]

Severe Hyperglycemia is defined as hyperglycemia (BG greater than [$>$] 300 mg/dL) with BG ketones greater than ($>$) 1.5 mmol/L, and/or accompanied by symptoms of nausea, vomiting or abdominal pain.

The meter and ketone test strips are supplied for the evaluation of ketone monitoring. Only blood ketones will be recognized (not urine ketones) for assisting in diagnosis of severe hyperglycemia. The monitors/test strips are quality controlled prior to dispensing to subjects. Blood ketones provide contemporaneous understanding of ketone levels associated with elevations in glucose.

Diabetic Ketoacidosis/DKA diagnostic criteria: BG greater than ($>$) 250 mg/dL, arterial pH less than ($<$) 7.3, bicarbonate less than ($<$) 15 mEq/L, moderate ketonuria or ketonemia and requiring treatment within a health care facility.^[6]

Hyperglycemic events will be recorded as DKA if the event includes the presence of all of the following:

- Arterial blood pH less than ($<$) 7.30 or serum bicarbonate less than ($<$) 15 mEq/L
- Blood glucose greater than ($>$) 250 mg/dL
- Serum ketones or large/moderate urine ketones
- Symptoms such as polyuria, polydipsia, nausea, or vomiting
- Treatment provided in a health care facility

Hyperosmolar Hyperglycemic State/HHS diagnostic criteria: BG greater than ($>$) 600 mg/dL, arterial pH greater than ($>$) 7.3, bicarbonate greater than ($>$) 15 mEq/L, minimal ketonuria and ketonemia and requiring treatment within a health care facility.^[6]

Hyperglycemic events will be recorded as HHS if the event includes the presence of all of the following:

- Arterial blood pH greater than ($>$) 7.3 or serum bicarbonate greater than ($>$) 15 mEq/L
- Blood glucose greater than ($>$) 600 mg/dL
- Negative/mild ketones
- Treatment provided in a health care facility

Adverse Event (AE) (ISO 14155:2020)

Untoward medical occurrence, unintended disease or injury, or untoward clinical signs (including abnormal laboratory findings) in subjects, users or other persons, whether or not related to the investigational medical device and whether anticipated or unanticipated.

Note 1 to entry: This definition includes events related to the investigational medical device or the comparator.

Note 2 to entry: This definition includes events related to the procedures involved.

Note 3 to entry: For users or other persons, this definition is restricted to events related to the use of investigational medical devices or comparators.

Adverse Device Effect (ADE) (ISO 14155:2020)

Adverse event related to the use of an investigational medical device.

Note 1 to entry: This definition includes adverse events resulting from insufficient or inadequate instructions for use, deployment, implantation, installation, or operation, or any malfunction of the investigational medical device.

Note 2 to entry: This definition includes any event resulting from use error or from intentional misuse of the investigational medical device.

Note 3 to entry: This includes 'comparator' if the comparator is a medical device

Serious Adverse Event (SAE) (ISO 14155:2020)

Adverse event that led to any of the following

- a) death,
- b) serious deterioration in the health of the subject, users, or other persons as defined by one or more of the following:
 - 1. a life-threatening illness or injury, or
 - 2. a permanent impairment of a body structure or a body function including chronic diseases, or
 - 3. in-patient or prolonged hospitalization, or
 - 4. medical or surgical intervention to prevent life-threatening illness or injury or permanent impairment to a body structure or a body function,
- c) foetal distress, foetal death or a congenital abnormality or birth defect including physical or mental impairment

Note 1 to entry: Planned hospitalization for a pre-existing condition, or a procedure required by the CIP, without serious deterioration in health, is not considered a serious adverse event.

Serious Adverse Device Effect (SADE) (ISO 14155:2020)

Adverse device effect that has resulted in any of the consequences characteristic of a serious adverse event

Unanticipated Adverse Device Effect (UADE) (21 CFR 812.3(s))

Any serious adverse effect on health or safety or any life-threatening problem or death caused by, or associated with, a device, if that effect, problem, or death was not previously identified in nature,

severity, or degree of incidence in the investigational plan or application (including a supplementary plan or application), or any other unanticipated serious problem associated with a device that relates to the rights, safety, or welfare of subjects.

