9.4.12 Risk Associated with SGLT Therapy

For subjects who are currently using SGLT inhibitors, the investigational center will provide training as well as a wallet card-formatted STICH protocol. The STICH protocol warns patients who are taking SGLT inhibitors about the risks associated with this therapy relative to the occurrence of ketosis and DKA.

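### The rules for recording DKA and HHS join pH and bicarbonate with *or* where the diagnostic criteria list both, so an event can be recorded as HHS against its own criteria or can meet both rules

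*Protocol*

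**What the plan says.** Protocol 11.2 (Definitions and Classification of Adverse Events) defines each condition twice.

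**DKA.** The diagnostic criteria line includes "arterial pH less than ($<$) 7.3, bicarbonate less than ($<$) 15 mEq/L, moderate ketonuria or ketonemia". The operational rule follows: "Hyperglycemic events will be recorded as DKA if the event includes the presence of all of the following". Its five items are:
- acid-base: "Arterial blood pH less than ($<$) 7.30 or serum bicarbonate less than ($<$) 15 mEq/L"
- glucose: "Blood glucose greater than ($>$) 250 mg/dL"
- ketones: "Serum ketones or large/moderate urine ketones"
- symptoms
- treatment in a facility

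**HHS.** The diagnostic criteria line includes "arterial pH greater than ($>$) 7.3, bicarbonate greater than ($>$) 15 mEq/L, minimal ketonuria and ketonemia". The operational rule again requires every item on its list:
- acid-base: "Arterial blood pH greater than ($>$) 7.3 or serum bicarbonate greater than ($>$) 15 mEq/L"
- glucose above 600 mg/dL
- ketones negative or mild
- treatment in a facility

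DKA and HHS incidence are separate safety summaries in Protocol 14.4.1.7 and SAP 7.3.1.8, and again for the run-in period. Under Protocol 12.2 the DMC reviews a separate rate of each per 100 patient-years. Neither document states how an event meeting both recording rules is counted. The SAP does not define the events itself.

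**The concern.** A recording rule should apply the criteria that stand above it. Here both acid-base items are looser than their criteria lines. Because both were loosened in the same way, the two rules are no longer mutually exclusive. Acidosis separates the two conditions in the criteria lines, yet under the recording rules a patient with a low pH can be recorded as HHS on the bicarbonate alone.

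At stake are two rare-event counts that are reported side by side. An event may be classed contrary to its own criteria line, may appear in both rows, or may be assigned differently by two sites or two adjudicators who each follow the text.

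**Working it through.** The plan gives no figure to reproduce, so the check is one of logic, followed by a simple sizing.

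**Step 1: acid-base items side by side (Protocol 11.2).**

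| | Criteria line | Recording rule |
|---|---|---|
| DKA | pH < 7.3, bicarbonate < 15, listed together | pH < 7.30 *or* bicarbonate < 15 |
| HHS | pH > 7.3, bicarbonate > 15, listed together | pH > 7.3 *or* bicarbonate > 15 |

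The complement of (pH < 7.3 or bicarbonate < 15) is (pH ≥ 7.3 and bicarbonate ≥ 15). The HHS recording item is wider than that, so any pair with one value high and the other low satisfies both acid-base items.

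**Step 2: HHS against its own criteria line.** Take glucose 700, pH 7.2, bicarbonate 18, negative ketones, treated in a facility.
- HHS recording rule: bicarbonate 18 > 15, glucose 700 > 600, ketones negative and facility treatment are all met. The event is recorded as HHS.
- HHS criteria line: pH 7.2 is not above 7.3. Not met.
- DKA recording rule: no ketones. Not met.

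**Step 3: both rules at once.** Take glucose 650, pH 7.32, bicarbonate 13, mild serum ketones, negative urine ketones, polyuria, treated in a facility.
- DKA recording rule: bicarbonate 13 < 15, glucose 650 > 250, serum ketones present, symptoms and facility treatment are all met.
- HHS recording rule: pH 7.32 > 7.3, glucose 650 > 600, ketones no more than mild and facility treatment are all met.

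The ketone item matters here. The DKA item names serum ketones without a level, and the HHS item allows mild ketones, so mild serum ketones fit both.

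**Step 4: enumeration.** The grid was pH {7.2, 7.3, 7.4}, bicarbonate {12, 15, 18}, glucose {200, 250, 400, 600, 700}, serum and urine ketones {negative, mild, moderate} and symptoms {no, yes}, with facility treatment assumed. That is 3 × 3 × 5 × 3 × 3 × 2 = 810 profiles. The number meeting both definitions was:

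| Acid-base wording | Serum ketones at any level | Serum ketones at least moderate |
|---|---|---|
| *or* in both rules (as written) | 4 | 0 |
| *and* in both rules | 0 | 0 |
| DKA *or*, HHS *and* | 0 | 0 |
| DKA *and*, HHS *or* | 0 | 0 |

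The four are pH 7.2 with bicarbonate 18, and pH 7.4 with bicarbonate 12, each at glucose 700 with mild serum ketones, symptoms, and urine ketones negative or mild. These counts show whether overlap is possible. They are not probabilities.

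**Step 5: what each repair leaves open.** With *and* in both rules, pH 7.2 with bicarbonate 18 meets neither definition: DKA fails on bicarbonate and HHS fails on pH. Under either wording, pH exactly 7.3 with bicarbonate exactly 15 meets neither. Setting a ketone level removes the overlap in Step 3 but not the contradiction in Step 2, where ketones are negative.

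**Step 6: size of one event.** At least 300 subjects are to enter the Phase 2 study period (Protocol 8.1, SAP 6).
- With 300 as denominator, one event is 1/300 = 0.33% of subjects in each row.
- The SAP's Safety Population is all enrolled subjects. Its size for Phase 2 is not given, but it cannot exceed the 575 planned for both phases, so the lower end is 1/575 = 0.17%.
- If 300 subjects each contribute 90 days (assumption), exposure is 300 × 90 / 365.25 = 73.9 patient-years. One event is then 100 / 73.9 = 1.35 per 100 patient-years in each rate.

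**The case against.** The strongest reply is that *or* alone does not produce the overlap. It also takes discordant pH and bicarbonate, glucose above 600 mg/dL, symptoms, and a DKA ketone item satisfied by mild serum ketones. If the moderate level in the DKA criteria line is meant to carry over to serum ketones, no profile meets both rules. That is correct, and it is why the ketone item belongs in the point. It does not remove the contradiction in Step 2.

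Second, *or* may have been chosen so that an event with only one of the two laboratory values could still be classified. The documents do not say so, but a plain change to *and* would have that cost.

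Third, the CEC reviews every reported DKA and HHS event, and where it disagrees with the investigator its adjudication is used for analysis (Protocol 12.1). This limits the harm. However, the CEC is asked whether it agrees with the investigator's classification, and the documents give it no DKA or HHS definition other than 11.2.

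A reader might infer three stronger things that the documents do not support.
- **A misclassified event could miss expedited review.** DKA and HHS are on the same lists for rapid sponsor notification (11.4), expedited CEC adjudication (12.1), DMC steps (12.2) and SmartGuard-related withdrawal (9.8).
- **A double count turns one event into two within one rate.** It adds one to each of two separate rates.
- **The glucose floor of 250 mg/dL wrongly excludes ketoacidosis in SGLT inhibitor users.** Protocol 9.4.12 says that the card it provides "warns patients who are taking SGLT inhibitors about the risks associated with this therapy relative to the occurrence of ketosis and DKA". But both DKA definitions agree on the floor, and no passage mentions ketoacidosis at lower glucose. That reading would rest on outside knowledge and a preference about the endpoint, so it forms no part of this point.

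**Conclusion.** The point holds as an internal contradiction in the event definitions. Both recording rules depart from their criteria lines, the HHS rule can record an event that its criteria line excludes, and one event can meet both rules with no stated precedence.

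The consequence is confined to counting. An affected event shifts a DKA or HHS row by one, or adds one to each, with the size per event given in Step 6. How often this would happen cannot be derived from the documents. It needs an unusual combination of values in an already rare event, and adjudication may catch it. DKA and HHS are descriptive summaries, so no hypothesis test, alpha or power is affected.

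The conclusion assumes that the recording items are applied literally and, for the overlap only, that mild serum ketones satisfy the DKA item. It is a clarification worth making before the Phase 2 safety tables are produced. It does not challenge the primary or secondary endpoints.

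**What to change.** - Reconcile each recording rule in Protocol 11.2 with the criteria line above it, for DKA and HHS alike: how pH and bicarbonate combine, and what serum ketone level is meant. The choice of clinical thresholds is the sponsor's.
- State how to classify an event with only one acid-base value available, and one whose two values point in opposite directions or fall on the boundary. Otherwise a move to *and* replaces double counting with unclassified events.
- State that an event meeting both rules is counted once, with the precedence fixed in advance for the CEC and repeated in the SAP safety summary sections.
- Apply the reconciled rule to the Phase 1 and Phase 2 summaries alike, so that the two phases stay comparable.

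**Cost.** This needs a wording amendment, with whatever regulatory and IRB steps Protocol 16.7 requires, and a check of any Phase 1 DKA or HHS events already adjudicated. No new data collection is needed. Counts may move by an event in either direction, and the study report should note any reclassification.

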11.3 Reporting of Adverse Events

The investigator or designee will record ALL AEs while the subject is enrolled in the clinical study. Each AE needs to be assessed for its device or procedure relatedness. A device related AE is associated with the use of the study devices (e.g., infection of sensor site or infusion set occlusion resulting in DKA). A procedure related AE is associated with testing related to the study procedures specified in the CIP (e.g., needle (blood draw) insertion pain).

Examples of device or procedure related AEs include:

- **Device** related (ADE): insertion site infection
- Serious adverse **device effect**: cellulitis at device insertion site requiring hospitalization
- **Procedure** related AE: bruising at needle (blood draw) insertion site

Subjects participating in the study have diabetes and are expected to experience hypoglycemia and or hyperglycemia. These normal events are not expected to be reported to sponsor as this is not considered an untoward event, but rather an expected occurrence. Any glycemic excursion that meets the protocol definition of severe hypoglycemia, severe hyperglycemia, HHS, or DKA is considered an untoward event and a worsening from the subject's baseline and would be reported to sponsor on an AE eCRF.

Baseline medical conditions should only be reported to sponsor on an AE eCRF if there is a worsening from the subject's baseline. For example, a subject previously diagnosed with asthma is hospitalized for severe asthma attack would be a reportable event.

Adverse events will be documented in the subject source file and reported to sponsor on an eCRF. The investigational center is responsible for documentation of AEs including obtaining source documents related to the event, such as emergency medical technician/paramedic reports, hospital records (admission summary; lab results, test results, discharge summary) or device uploads to support the event. Source documents will be reviewed to determine if additional AEs have occurred and require reporting.

Adverse events that have not resolved at the time of the subject's discontinuation or completion of the study should have an "outcome" of Not Recovered/Not Resolved at study end in subject source and on an eCRF. The investigator should ensure that subject is aware of any follow-up or additional treatment that is required for any ongoing AE at EOS participation; however, there will be no eCRF entry for the ongoing follow-up.

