
Risks with the use of an insulin infusion pump may include the risk of malfunction of the components of the system (pump, software, infusion set and reservoir) as well as the risk of use error during use of the system. DDs or use errors can result in administration of too much or too little insulin which can lead to the following clinical consequences:
 
 • Hypoglycemia • Hyperglycemia • Diabetic ketoacidosis or HHS • Severe hypoglycemia with or without associated seizure, coma or death • Kinked cannula leading to hyperglycemia • Infusion set disconnection from pump leading to hyperglycemia • Subject removes the reservoir from the pump but forgets to disconnect the infusion set from the body which results in hypoglycemia or severe hypoglycemia • Dislodged cannula leading to hyperglycemia • A pump error may lead to under delivery or over-delivery of insulin • Battery failure – no insulin delivered • Insulin deterioration leading to hyperglycemia • Incomplete priming; fails to prime tubing and/or cannula, leading to hyperglycemia 	
Prevention and mitigation include:
 
 • Follow the provided user guides & instructions for insulin and insulin pump management which includes information on infusion set change. • Train prior to study device use on appropriate device use and diabetes management principles and instruct to call investigator with problems. • Instruct to check their meter glucose if their high or low symptoms do not match their sensor alerts or SG readings in order to make diabetes treatment decisions. • Instruct to check their meter glucose if there are any concerns that the SG value is not accurate. • Instruct to have glucose and glucagon on hand for hypoglycemia. • Instruct to change infusion set if suspected catheter occlusion or administer insulin with syringe for persistent hyperglycemia especially if ketones develop.

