
 • Hypoglycemia • Severe hypoglycemia • Hyperglycemia • Diabetic ketoacidosis or HHS • User entry error 
 ○ Patient administering boluses by entering false carb doses leading to hypoglycemia or hyperglycemia ○ Patient entering false glucose values for any reason leading to hypoglycemia and hyperglycemia ○ Patient entering false BG values for calibration leading to hypoglycemia or hyperglycemia • Sensor failure resulting from patient failure to calibrate leading to hypoglycemia or hyperglycemia • Sensor over-reading resulting in hypoglycemia • Sensor under-reading resulting in hyperglycemia • Sensor missed transmission, or any other fault resulting in no SG value, leading to hyperglycemia or hypoglycemia • Voluntary insulin delivery (with the pump or with a syringe) immediately prior to entering SmartGuard may result in severe hypoglycemia despite shutting down insulin delivery by the algorithm • Hypoglycemia related to patient taking insulin via injection while in Closed Loop (SmartGuard) • Hypoglycemia or hyperglycemia related to entering or exiting Closed Loop (SmartGuard) • Insulin over-delivery due to potential interference from acetaminophen • Cyber security hacking into pump 	
 • Instruct to avoid the use of products containing acetaminophen. • If acetaminophen is taken, subjects will be instructed to use additional BG meter readings to verify their glucose levels. • If acetaminophen is taken, while the SmartGuard feature is active, subjects will be instructed to use the temp target feature (when used, Auto Correction is not available). • Instruct subjects that in case of prolonged use of acetaminophen, the temp target feature can be used repeatedly and in succession. • Pump has cybersecurity encryptions to prevent hacking.

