12.2 Data Monitoring Committee

A data monitoring committee (DMC) consisting of external physicians with an expertise in Endocrinology and the management of insulin-requiring diabetes including CGM, along with an external statistician will be convened to review study progress and safety. The Board will convene approximately every 90 days. The Board will also meet when ad hoc review is required.

The DMC will perform 4 main functions:

First: DMC will track and trend the overall safety of the study.

Event rate, defined as number of events per 100 patient years will be reviewed by the DMC with respect to the following:

- Event rate of all SAEs
- Event rate of severe hypoglycemia
- Event rate of severe hyperglycemia
- Event rate of DKA
- Event rate of HHS
- Event rate of device related AEs

Second: Based on their meetings, DMC will recommend a decision to the sponsor regarding the following:

- Whether or not enrollment should be halted.
- Whether or not the entire study will need to be stopped including for those subjects who have received study devices already.

Note: If it is decided to withdraw subjects from participation in the study or if the study is stopped, subjects will be followed-up in accordance with standard practice by their own providers.

Third: During the study, the following steps will be taken for:

- UADE

- Device related DKA
 - Device related HHS
 - Device related Severe Hypoglycemia
1. Investigational center staff will notify the sponsor within approximately 24 hours of investigator or study coordinator awareness of events described above.
 2. Sponsor will notify the FDA within approximately 3 business days of awareness of the event and provide updates to the agency as information becomes available.
 3. DMC is to meet within 10 business days from CEC adjudication of the event. The investigator should be available to answer questions from DMC, as needed.
 4. Based on their review, DMC will recommend that the sponsor make a decision regarding the following:
 - a) Whether or not subject enrollment may continue
 - b) Whether or not new subject enrollment should be suspended, with enrolled subjects continuing in the study.
 - c) Whether or not the entire study should be stopped, including those subjects who have already received study devices.

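### Section 11.3 sorts glycemic excursions by severity alone, so non-severe ones caused by a documented device fault can go missing from the DMC's device-related AE rate

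*Protocol*

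**What the plan says.** Protocol Section 11.3 tells sites to record all AEs. It then notes that subjects with diabetes will have hypo- and hyperglycemia, and says: "These normal events are not expected to be reported to sponsor as this is not considered an untoward event, but rather an expected occurrence". The next sentence draws the line: "Any glycemic excursion that meets the protocol definition of severe hypoglycemia, severe hyperglycemia, HHS, or DKA is considered an untoward event", and such an event goes on an AE form. The cause of the excursion is not mentioned.

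Four other places bear on the same events.

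- **Section 11.2** defines an AE without regard to whether it was anticipated. It defines an adverse device effect (ADE) as an AE related to device use, sets no severity threshold, and includes AEs from "or any malfunction of the investigational medical device". On use error it adds: "This definition includes any event resulting from use error or from intentional misuse of the investigational medical device".
- **Section 10.1, Table 4** says "DDs or use errors can result in administration of too much or too little insulin which can lead to the following clinical consequences", and the list that follows gives plain hypoglycemia and severe hypoglycemia as separate entries. It also names "A pump error may lead to under delivery or over-delivery of insulin" and "Sensor over-reading resulting in hypoglycemia".
- **Section 9.1.1, Table 3** tells sites to record a deterioration of an existing condition and gives glycemic problems as an example.
- **Section 13** has every device deficiency reported to Technical Support documented, and has sites review the call reports for possible AEs.

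Section 12.2 lists six event rates per 100 patient-years for the DMC. One is "Event rate of device related AEs".

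**The concern.** Wrong insulin delivery is the most direct way in which an automated insulin system can do harm, and its first result is a low or a high that the subject corrects. Section 11.3 does not say how such an event is recorded when a device fault has been identified as the cause. A site that follows the severity line leaves it off the AE form.

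The other five DMC rates cover SAEs, severe hypoglycemia, severe hyperglycemia, DKA and HHS. The device-related AE rate is therefore the only listed one that could show non-severe glycemic harm from a fault. The trial has a single arm, so no comparator would reveal under-recording. Sensor data show that a low occurred but not that a fault caused it. With up to 40 centers, sites may also resolve the difference between Table 3 and Section 11.3 in different ways.

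**Working it through.** The plan gives no figure to reproduce. The check is a comparison of texts, followed by the arithmetic of the rate.

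**1. Which excursions fall below the line.** Section 11.2 defines severe hypoglycemia as needing another person's help because of altered consciousness. Severe hyperglycemia is BG above 300 mg/dL with ketones above 1.5 mmol/L and/or nausea, vomiting or abdominal pain. DKA and HHS have their own criteria. What remains is mainly self-treated hypoglycemia, and hyperglycemia without raised ketones or those symptoms. An excursion that meets SAE criteria is still reported under Section 11.4.

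**2. One event followed through the plan.** Suppose a sensor over-reads, the pump over-delivers, and the subject treats the low alone.

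| Place | Treatment of the event |
|---|---|
| Table 4 | A listed device risk |
| 11.2 | Being anticipated does not exclude it; no severity threshold for an ADE; malfunction included |
| 13 | Fault documented as a device deficiency; call report checked for a possible AE |
| 11.3 | Meets none of the four severe definitions; nothing makes it reportable because of its cause |
| Table 3 | Could be recorded as a glycemic problem |
| 12.2 | Counted only if it was recorded as an AE |

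The fault is kept. Whether its glycemic consequence becomes an AE depends on which of these texts the site follows.

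**3. Whether another section settles it.** The glycemic examples of device relatedness are all severe: an occlusion leading to DKA in 11.3, and a severe hyperglycemia AE in 11.6. The CEC list in 12.1 contains only serious, unanticipated or severe categories. The sponsor's assessment in 11.7 of whether an event was anticipated starts from an AE already judged device-related. None of these says how a non-severe excursion with a documented fault is recorded.

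**4. Effect on the rate.** Rate = 100 × recorded device-related AEs / patient-years. An unrecorded event adds 0 to the numerator, while the subject's time stays in the denominator, so the bias can only be downward.

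For scale, take the planned minimum of 300 subjects entering the Phase 2 study period and its roughly 90 days:

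300 × 90 / 365.25 = 73.9 patient-years

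100 / 73.9 = 1.35

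On that denominator each unrecorded event lowers the rate by about 1.35 per 100 patient-years. This assumes exactly 300 subjects, complete follow-up and no run-in time. More subjects or added run-in time would make the step smaller; an early DMC review with less patient time would make it larger. The documents do not say how many such events to expect, so the total bias cannot be computed.

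**The case against.** The strongest reply is that 11.3 exempts only the ordinary events of diabetes. A low caused by over-delivery is not obviously ordinary, and the sentence calling severe events untoward does not say that only those are. The ADE definition also presupposes an AE. If an excursion is not untoward it is neither an AE nor an ADE, and if it is untoward the instruction to record all AEs applies. On that reading there is no flat contradiction.

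This reading is possible, and it rules out a stronger claim that a reader might infer: that the protocol forbids recording every non-severe excursion even when a device error caused it. The text does not say that. But it does not state the narrower reading either, and the only line it draws is severity. The ambiguity stands.

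Several further points stand in full. Device deficiencies are documented (Section 13) and summarised (Protocol 14.4.1.5, SAP 7.3.1.6), so the fault is not lost. The severe hyperglycemia definition is broad and will catch many symptomatic infusion-set or pump failures. The primary safety endpoint is HbA1c change. The individual event types named in the stopping rules, which also get expedited review, are UADEs and device-related DKA, HHS and severe hypoglycemia. None of these is affected. Exempting ordinary excursions is a reasoned choice that should be kept.

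**Conclusion.** The point holds in a limited form. Section 11.3 makes no provision for a non-severe excursion caused by a documented device fault, and it is not reconciled with 11.2, Section 13 or Table 3. The demonstrable consequence is a downward bias in one of the six DMC rates. This assumes that at least some sites apply the severity line as written and that at least some such events occur.

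Two larger conclusions are not supported. One is that final ADE totals are biased: the visible safety lists (Protocol 14.4.1.7, SAP 7.3.1.8) contain SAEs, SADEs, UADEs and the severe glycemic events, but no overall ADE count. The other is any estimate of how many events are missed: the documents give no rate. The size is unknown, and the change is a cheap improvement.

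**What to change.** Add one sentence to Section 11.3 along these lines: *A hypo- or hyperglycemic excursion that meets none of the severe definitions is nevertheless recorded as an AE and assessed for device relatedness when a documented device deficiency is judged its probable or causal explanation under Section 11.6. Documentation means a Technical Support report or CareLink review showing a malfunction, a false sensor value, or over- or under-delivery.*

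State that the exemption for all other non-severe excursions remains, and make 11.2, Section 13 and Table 3 point to this rule.

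A merely possible relationship should not trigger recording. Section 11.6 puts weak relationships and unassessable cases in that category. In a system that doses continuously from sensor values, that could take in a great many ordinary lows and highs and so defeat the exemption.

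The cost is a short protocol amendment, site retraining, some additional AE forms and a slightly less favourable device-related AE rate. Technical Support reports and CareLink uploads are already collected, so no new data source is needed.
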